6.2 Safety Endpoints and Evaluations

Safety assessments comprise the collection of data on adverse events, dose reductions, over-doses, dose interruptions and treatment discontinuations.

6.2.1 Adverse Events and Special Situations

The collection and reporting of AEs and Special Situations (SS) will follow regulations related to non-interventional studies.

The definition of AEs and SAEs can be found in Section 9.1. For the management and reporting of the AEs and SS, please refer to Section 9.

All AEs, whether they are serious/nonserious, related/unrelated, and all SS should be collected throughout the observation period of cabozantinib treatment. After cabozantinib treatment has ended, only serious/nonserious AEs that are related to cabozantinib, as assessed by the investigator, that occur during the 3-month follow-up period are collected. All AEs will be assessed according to incidence, intensity/grade, causality, outcome, action taken and seriousness.

The investigator and any qualified designees are responsible for detecting, documenting, and recording events that meet the definition of an AE or SAE and remain responsible for following up any AEs or SAEs.

PAGE 31/52

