Abbreviations: AE=Adverse Event; CR=Complete Response; DCR=Disease control rate; ECOG=Eastern Cooperative Oncology Group; eCRF=electronic Case Report Form; EORTC=European Organisation for Research and Treatment of Cancer; EoS=End of Study; FU=Follow-Up; HrQoL=Health-related Quality of Life; NETs=Neuroendocrine tumours; PD=Progressive Disease; PR=Partial Response; PSP=Patient Support Program; QLQ-C30=Core Quality of Life Questionnaire; QLQ-GINET21= Quality of Life Questionnaire module for GI-NET patients; SD=Stable Disease; TA=Tumour Assessment.

IPSEN GROUP CONFIDENTIAL CONFIDENTIAL

PROTOCOL FINAL V1.0: 30 JULY 2025 PAGE 22/52

All data will be recorded as applicable and available during standard of care routine: if a specific diagnostic procedure is done according to clinical routine the corresponding data should be recorded in the eCRF, otherwise the corresponding part of the eCRF will be marked as not done.

- ^a EoS visit for participants still on cabozantinib treatment after 18 months.
- ^b Combined FU/EoS visit for participants who discontinued cabozantinib early (up to 15 months after Visit 1) and subsequent therapy switch.
- ^c Enrolment in the study is possible if cabozantinib treatment started up to 4 weeks prior to enrolment. See Section 4.1.
- ^d Clinical and/or TA via imaging to determine SD, PR, CR and PD. The type of assessment must be recorded in the eCRF.
- ^e The baseline radiological tumour assessment should be the most recent TA prior to enrolment.
- ^f In case of PD and cabozantinib treatment discontinuation and subsequent therapy switch, only the FU visit must be performed 3 months after end of cabozantinib treatment. Of note, cabozantinib treatment beyond progress is possible; in this case the participant is not passed over to the FU period but remains in the 18-month observation period. In addition, also other reasons e.g. drug intolerability or adverse events might lead to cabozantinib treatment discontinuation and switch to subsequent treatment; in these cases, also only the FU visit must be performed 3 months after end of cabozantinib treatment.
- g Including recording of dose modifications, overdoses, treatment interruptions and permanent study discontinuations along with the reason for discontinuation.
- h Performed if participant was enrolled up to 4 weeks after first dose of cabozantinib and Visit 1 was captured retrospectively. HrQoL baseline will then be taken.

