- ¹ Supporting measures include the recording of participation in a PSP, use of psycho-oncological support or nutritional advice.
- ^j In particular, start of new treatment, type of treatment, treatment line and DCR within 12 weeks. For the determination of the DCR after therapy switch, the last TA prior to therapy switch serves as the baseline TA.
- ^k Only AEs related to cabozantinib as assessed by investigator.

PAGE 23/52

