 - by the investigator (clinical and radiographic). If radiological assessment is performed, it should be indicated whether the assessment of progression is based on Response Evaluation Criteria in Solid Tumours 1.1 guidelines (RECIST 1.1) or local standard of care. The most recent radiographic assessment performed before the visit is to be reported with the date and overall response. If clinical assessment is performed, the date of progression is to be provided if applicable. An assessment via imaging is expected approximately every 3 months as per standard of care.
- ECOG performance status.
- Cabozantinib regimen:
 - (Start date, stop date, administered dose, frequency, primary reason for dose change or discontinuation).
- Clinical characteristics:
 - weight, systolic and diastolic blood pressure; heart frequency.
- NET biochemical markers:
 - CgA.
 - NSE.
- EORTC QLQ-C30 and QLQ-GINET21 questionnaire every 3 months until the last visit while taking cabozantinib.
- Supporting measures (see Visit 1).
- Concomitant NET medication (including concomitant medications for AEs).
- Concomitant non-drug NET therapy.
- Adverse Events and Special Situations:

PAGE 26/52

- From Visit 1 onwards until the End of Study (EoS), treatment-emergent nonserious AEs and SAEs and SS including pregnancy occurring during the data reporting period at each visit will be reported. Any clinically significant (CS) findings (as assessed by the investigator) on physical examination, laboratory values and electrocardiograms (ECGs) performed as per routine/ standard clinical practice will be reported as AEs.

If a participant withdraws consent, data will be collected up to the time of withdrawal, with no additional information collected thereafter.

Post-cabozantinib Treatment Follow-up Period:

For participants who discontinued cabozantinib during the first 15 months of observation, a follow-up visit at approximately 3 months after discontinuation should be documented, as the next standard of care visit for the next LoT is expected.

The following data will be collected:

- Date of visit/contact.
- ECOG Performance Status.
- Subsequent treatment following cabozantinib discontinuation including sequences of treatment, drug names and DoT, and reasons for end of treatment line.
- New nonserious AEs and SAEs assessed as related to cabozantinib (Adverse Drug Reactions (ADRs)) that start during the Post-Treatment Follow-up Period.

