- Tumour assessment by the investigator (clinical and radiographic). If radiological assessment is performed, it should be indicated whether the assessment of progression is based on RECIST 1.1 or local standard of care. The most recent radiographic assessment performed before the visit is to be reported with the date and overall response. If clinical assessment is performed, the date of progression is to be provided if applicable.
- Concomitant medications for treatment of ADRs and changes to concomitant medications for treatment of pre-existing medical and surgical conditions (i.e. medical/ surgical history) at the time of occurrence of ADRs. Only AEs related to cabozantinib as assessed by the investigator will be collected, see above.
- Any further follow-up information for ongoing AEs (until resolution or stabilisation) and SS including pregnancy that occur during the Treatment Period.

If a participant is lost to follow-up during the Post-treatment Follow-up Period, multiple attempts should be made to contact the participant or designee, which should be documented in the participant's records.

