8.4.4 Safety Analysis

Safety analyses will be performed on the Safety population.

During the Treatment Period (Visit 2 to Visit 9), all treatment-emergent AEs including nonserious AEs and SAEs and SS including pregnancy will be collected.

Analysis of AEs

A treatment-emergent AE is defined as any AE that occurs after the first dose of study treatment if:

- It was not present prior to receiving the first dose of study treatment; or
- It was present prior to receiving the first dose of study treatment but the intensity increased during the active phase of the study.

The focus of analysis of this study will be the duration of the Treatment Period, i.e. up to 30 days after the permanent discontinuation of cabozantinib.

An overall summary table of all AEs (including fatal events) will be presented with the number and proportion of participants and the number of events, including frequency of SAEs, drug-related AEs and drug-related SAEs. Summary incidence tables of all AEs, SAEs and AEs by relationship and intensity/grade to study drug will be provided, classified by primary System Organ Class (SOC) and Preferred Term (PT).

All AEs will be coded according to the Medical Dictionary for Regulatory Activities (MedDRA) and will be classified by MedDRA PT and SOC.

All safety data will be included in the participant data listings, such as listings of all AEs, SAEs, AEs leading to study drug withdrawal, AEs leading to dose reduction or interruption and listings of deaths.

Analysis of "Special Situation"

SSs will be listed separately, and summary incidence tables will be provided. The AEs associated with SSs will be described.

PAGE 37/52

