9.1.4 Adverse Events of Special Interest

Not applicable

9.2 Time Period and Frequency for Collecting and Reporting AE, SS and SAE Information

For the definition of the AEs and SS, please refer to Section 9.1.

During the Treatment Period, (i.e. from Day 1 until 30 days after discontinuation of cabozantinib treatment or EoS), all AEs including nonserious AEs and SAEs, and SS will be collected. During the Post-treatment Follow-up Period (i.e. from 30 days after discontinuation of cabozantinib treatment until the EoS), only new AEs assessed as related to cabozantinib that start during this period will be collected. Incidence of pregnancy will be collected until 5 months after EoS. If possible, pregnancy should be followed up until the outcome is known. Any further follow-up information on ongoing AEs (until resolution or stabilisation) and SS including pregnancy that occurred during the Treatment Period will be collected.

PAGE 42/52

From this point onwards, the term 'Safety Report' will collectively refer to all reports of non-serious related AEs, SAEs, fatal outcomes and SS.

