9.2.1 Collection of the AEs/SAEs/SS in the eCRF

The collection and reporting of AEs will follow regulations related to non-interventional studies.

All AEs, whether they are serious/nonserious, related/unrelated, and all SS should be collected in the eCRF during the course of the study. Adverse events will be assessed according to incidence, intensity/grade, causality, outcome, action taken and seriousness.

All AEs will be collected in the eCRF from the first intake of cabozantinib until study completion, i.e. EoS or the EoS/follow-up visit, as specified in Table 4-1.

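### Three inconsistent rules govern AE collection after cabozantinib stops, and the one in Section 6.2.1 does not supply the 30-day window analysed in Section 8.4.4

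*Protocol*

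**What the plan says.** The protocol sets AE collection after the last dose in several places.

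- **Section 6.2.1.** All AEs are collected during treatment. Then: "After cabozantinib treatment has ended, only serious/nonserious AEs that are related to cabozantinib, as assessed by the investigator", through the 3-month follow-up.
- **Table 4-1, footnote k**, attached to the follow-up visit: "Only AEs related to cabozantinib as assessed by investigator".
- **Section 9.2.** The Treatment Period is defined as "from Day 1 until 30 days after discontinuation of cabozantinib treatment or EoS), all AEs" being collected. The Post-treatment Follow-up Period starts at day 30, and from then only new related AEs are collected.
- **Section 9.2.1.** "All AEs will be collected in the eCRF from the first intake of cabozantinib until study completion", explained as the end-of-study or the combined end-of-study/follow-up visit. Related and unrelated events are both included. The sentence closes by referring to Table 4-1.
- **Section 4.5, follow-up list.** New related AEs "that start during the Post-Treatment Follow-up Period". A later item on concomitant medication adds: "Only AEs related to cabozantinib as assessed by the investigator will be collected, see above".

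Section 8.4.4 places the focus of the safety analysis on the Treatment Period, "up to 30 days after the permanent discontinuation of cabozantinib", and plans incidence tables of all AEs and all SAEs as well as tables by relationship.

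**The concern.** The rule for entering data and the window for analysing them should match. Here a site can follow one section of the protocol faithfully and never enter events that another section says will be tabulated. Events that were never collected cannot be recovered by any later analysis rule, so this is not something that the SAP can settle.

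Incidence of all AEs and of all SAEs is a listed secondary endpoint. With up to 50 sites, those two rates would depend partly on which section each site works from. In a single-arm study there is no comparator in which the same under-recording would show. Whether an unrelated event is entered would also rest on the investigator's causality judgement.

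**Working it through.** The protocol gives no figure to reproduce, so the check sets the rules side by side by time since the last dose.

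| Source | Unrelated AEs, days 1–30 | Unrelated AEs, day 31 to follow-up visit | Related AEs after stopping |
|---|---|---|---|
| 6.2.1 | not collected | not collected | collected |
| 9.2 | collected | not collected | collected |
| 9.2.1 | collected | collected | collected |
| Needed for 8.4.4 | yes | no | yes, to day 30 |

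1. **The rules differ.** The three rows for 6.2.1, 9.2 and 9.2.1 are all different, so these are three rules and not one rule worded three ways.
2. **Match to the analysis.** Section 9.2 supplies exactly the 8.4.4 window. Section 9.2.1 supplies it and more. Section 6.2.1 leaves the days 1–30 cell for unrelated events empty.
3. **Footnote k.** It governs the follow-up visit about 3 months after stopping. Footnote f says that after stopping and switching "only the FU visit must be performed 3 months after end of cabozantinib treatment". Read literally, the only required visit at which days 1–30 could be documented is therefore limited to related events, and footnote k repeats the 6.2.1 rule. Read together with 9.2, it may cover only events that start after day 30.
4. **Section 9.2.1 against Table 4-1.** Section 9.2.1 keeps unrelated events up to the follow-up visit but cites the table whose footnote k excludes them at that visit. The section is in tension with its own reference.
5. **Section 4.5.** Its first AE item refers to the Post-Treatment Follow-up Period, which 9.2 starts at day 30. That item agrees with 9.2. The sentence in the concomitant-medication item has no time limit of its own and points back to that item.
6. **SAEs.** Section 9.2.2 requires all SAEs, whatever their causality, to be reported within 24 hours, with eCRF collection tied to the observation period. Take an unrelated SAE 10 days after the last dose. Under 9.2 it is collected and reported. Under 6.2.1 it is not collected, although 9.2.2 may still bring it in.
7. **Related events.** The last column is the same under every rule, so counts of drug-related AEs and drug-related SAEs do not depend on the rule followed.

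**The case against.** The strongest defence is that Section 6.2.1 itself sends the reader to Section 9 for AE management and reporting, and that 9.2 is the section titled for the collection period. A careful site would then follow 9.2. This carries some weight, but 6.2.1 goes on to state its own explicit rule, and Section 9 does not speak with one voice, because 9.2 and 9.2.1 disagree from day 31 onwards.

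Three further points stand and limit the finding:

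- Section 9.2.2 makes loss of unrelated SAEs less certain than loss of unrelated nonserious AEs. It does not remove the risk, because Section 4.7 runs the observation period to Visit 9 while describing participants who stop and switch as passing into follow-up. Whether days 1–30 still count as observation is left open for them.
- Two of the three frequencies singled out in Section 3 are drug-related, and these are untouched.
- A reader might count footnote k as a second rule that loses events. The documents do not support that: it echoes 6.2.1 at most, and it has a reading compatible with 9.2.

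A reader might also infer that the lost events would be many because AEs and deaths gather around discontinuation. Nothing in the protocol says so. Deaths have their own form in Table 4-1, and under Sections 9.1.1 and 9.1.2 expected progression is not an AE and death from progression is not an SAE.

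**Conclusion.** The contradiction is real and should be corrected. One of the three rules, that of 6.2.1 (with footnote k if read literally), fails to supply the window in 8.4.4. Sites following it would omit unrelated AEs, and possibly unrelated SAEs, in the 30 days after stopping. All-AE and all-SAE incidence would be under-ascertained and site-dependent.

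The size of the loss cannot be derived, because the documents give no rate of unrelated AEs after stopping and no indication of how many sites would follow which section. It is tempting to build a figure from the median treatment durations quoted in Section 2.3 (8.3 months for pNET, 5.5 for epNET). With 30 days taken as 0.986 month, the window is 0.986/(8.3 + 0.986) = 11% to 0.986/(5.5 + 0.986) = 15% of the treatment-emergent period for a participant at the median. Under an assumed exponential duration, 1 − 2^(−18/8.3) = 78% to 1 − 2^(−18/5.5) = 90% would stop within 18 months. These are shares of time and of participants exposed to the ambiguity, not shares of events lost. The second pair also counts participants who stop because they die, who have no 30-day window. Neither pair should be read as an effect size.

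**What to change.** Use the protocol's own Section 9.2 rule throughout, since it already matches 8.4.4: all AEs and SAEs, related or not, from first intake to 30 days after discontinuation, and after that only new related AEs.

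- **6.2.1:** move the start of the restriction from the end of treatment to day 30.
- **Table 4-1, footnote k:** state that the restriction applies to events starting after day 30, so that unrelated events from days 1–30 can still be entered at the follow-up visit.
- **9.2.1:** end the collection of unrelated events at day 30, and make the reference to Table 4-1 consistent with the revised footnote.
- **4.5:** the first AE item can stay. Check that the sentence in the concomitant-medication item reads consistently with it.

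The cost is protocol wording and slightly more AE entry in the month after stopping. Only the collection of safety data changes, not the management of participants.

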6.2.2 Other Safety Endpoints

Not applicable.

6.2.2.1 Physical Examination

Not applicable.

6.2.2.2 Vital Signs

Evolution of weight and blood pressure over time.

6.2.2.3 Clinical Safety Laboratory Assessments

Not applicable.

6.3 Quality of Life/Standardised Questionnaires

Patient reported outcomes on hrQoL are assessed with the validated 30-item EORTC QLQ-C30 (28 questions with a 4-point Likert scale and two questions with a 7-point Likert scale) and 21-item QLQ-GINET21 questionnaires (21 questions with a 4-point Likert scale). Global and subscale scores are determined by the official scoring algorithm.

QoL-related endpoints are:

- QLQ-C30 global and subscale scores for each visit at which hrQoL was assessed.
- QLQ-GINET21 subscale scores for each visit at which hrQoL was assessed.

6.4 Medical Resource Utilisation

Not applicable.

6.5 Exploratory Endpoints

Supporting measures:

Frequency and type of supporting measures at each visit these measures were assessed.

Correlation analyses:

Assessment of a potential correlation between the investigated parameters, specifically:

- Effectiveness outcomes and occurrence of AEs.
- Effectiveness outcomes and dose reduction.
- HrQoL and dose reduction.
- HrQoL and supporting measures.
- Supportive measures and DoT/treatment discontinuation due to AEs.
- Dose reduction and DoT.
- HrQoL and DoT.

See more details in Section 8.4.3.3.

PROTOCOL FINAL V1.0: 30 JULY 2025

PAGE 32/52

7 TREATMENTS OF INTEREST

This is an observational study designed to collect data on the use of Cabometyx $^{\mathbb{R}}$ (cabozantinib) in real-world clinical practice.

The decision to prescribe cabozantinib will be made prior to and independently of the decision to enrol the patient in this non-interventional study.

PAGE 33/52

8 STATISTICAL CONSIDERATIONS

The information provided in this section may be subject to changes that will be indicated in the final Statistical Analysis Plan (SAP) of this study. The SAP will be developed as a separate document and approved prior to database lock, containing a description of the planned statistical analysis in detail with Tables, Figures and Listings (TFLs) templates.

8.1 Participant Classification and Definitions

Enrolled participant: Eligible participant who is fully informed about the study and

who has given written informed consent to participate (before

any study data is collected).

Treated participant: Enrolled participant who received at least one intake of

cabozantinib during the study.

Switched participant: Treated participant who permanently discontinued cabozan-

tinib treatment and switched to a subsequent LoT.

Withdrawn participant: Participant who ceased participation in the study prior to the

planned follow-up of the study.

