4.1 Overview

This is an international, multicentre, non-interventional, prospective, single-arm study. This study will be conducted in up to 50 centres in Austria and Germany. A total of 150 participants will be included in the study. Participants will be treated and monitored in accordance with usual medical practice during their participation in this study.

The expected duration of the recruitment period will be 18 months. Participants will be followed for a maximum of 18 months (observation period) while they receive cabozantinib as per the SmPC.

Participants prematurely discontinuing cabozantinib (i.e. within the first 15 months of observation period) and initiating a subsequent treatment will be followed up approximately 3 months after the treatment switch to collect effectiveness data for the new LoT. Enrolment in the study is possible if cabozantinib treatment started up to 4 weeks prior to enrolment. The data for Visit 1 will be captured retrospectively and starting at Visit 2 data will be collected prospectively including hrQoL baseline assessment.

To avoid selection bias in participant recruitment, investigators will offer enrolment to all eligible participants consecutively to achieve their recruitment target during a restricted and defined period. This includes patients who have stopped cabozantinib treatment within their first 4 weeks to avoid selection bias. But, if consecutive enrolment is not feasible (e.g. administrative constraints), an alternate enrolment schedule will be permitted and will have to be documented before the first participant is enrolled. The investigators will have to follow the same recruitment pace until achievement of his/her recruitment target.

4.2 **Population Characteristics**

One hundred and fifty (150) adult participants with unresectable or metastatic, well -differentiated epNET and pNET who have progressed following at least one prior systemic therapy other than SSA, and who are prescribed cabozantinib tablets according to the SmPC prior to entry into the study will be included in Austria and Germany.

Further details of the study population are provided in Section 5.

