4.5 Study Data Collection Timing and Methods

The expected duration of the study is maximum of 36 months. The expected duration of recruitment is 18 months. Participants will be followed-up for up to 18 months of cabozantinib treatment. If cabozantinib is discontinued during the first 15 months of observation, and a subsequent therapy is started, a follow-up visit will be performed approximately 3 months after discontinuation of cabozantinib. Enrolment in the study is possible if cabozantinib treatment started up to 4 weeks prior to enrolment. The data for Visit 1 will be captured retrospectively. Starting at Visit 2 data will be collected prospectively including hrQoL baseline assessment. Patients who have started cabozantinib treatment up to 4 weeks before giving informed consent but stopped treatment during the 4 weeks may be included.

Three visit types will be performed:

- Baseline Inclusion/ Treatment Initiation Visit (Visit 1)
- Regular visit during the observational period (Visits 2 to 9) approximately every month until Month 3 and every 3 months afterwards
- Follow-up visit for participants discontinuing cabozantinib treatment during the 15-month observational period

All data will be recorded as applicable and available during standard of care routine. If a specific diagnostic procedure or assessment is done according to clinical routine the corresponding data should be recorded in the eCRF, otherwise the corresponding part of the eCRF will be marked as not done / not available.

The timing of the visits according to routine clinical practice is assumed to be close to the proposed schedule. If the timing does not meet the schedule, entries should be made at the visit nearest in time to the proposed schedule.

For regular visits during the observation period the minimum information that must be recorded is the most recent result of the tumour assessment at/before Visit 1 to obtain a baseline value required for determination of the primary endpoint, DCR. Minimum required information for follow up visits after therapy switch, i.e. starting a new LoT includes the start date of new treatment (partial dates are allowed) and the type of treatment.

Adverse events (including treatment-emergent nonserious AEs and serious adverse events (SAEs)) and Special Situations (SS) including pregnancy will be collected during the observation period, see Section 9.

Inclusion/Treatment Initiation (Visit 1)

The following data will be collected:

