4.7 Study Duration/Observation Period

The expected study duration is 3 years, with an 18-month enrolment period from first participant, first visit. The EoS is expected to be a maximum 18 months after the last participant has been enrolled.

The study will be considered to have started when the first participant has signed informed consent.

The study will be considered to have ended after the last participant's data has been collected.

The study observation period starts from participants signing the informed consent and continues until Visit 9 (Month 18). Participants discontinuing cabozantinib treatment and starting a new LoT during the first 15 months of cabozantinib treatment are passing over into the follow-up, which is approximately 3 months after discontinuation of cabozantinib.

Participants will be followed until the end of observational period (i.e. a maximum of 18 months after Visit 1) or withdrawal of consent, or death, whichever occurs first.

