8.2 Definition of Analyses Populations

Enrolled population: All participants enrolled.

Full Analysis Set (FAS) / A Safety population

All eligible participants treated with cabozantinib within this

non-interventional study.

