8.2.2 Participant Allocation and Reasons for Exclusion from the Analyses

The rules for the allocation of participants to each of the analysis populations will be defined and documented during a data review meeting held prior to database lock.

During the data review meeting, based on minor or major protocol deviations recorded, participants may be excluded from the safety/FAS population.

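### The FAS/Safety set is tied to cabozantinib intake during the study, which read literally drops patients who stopped before consent, whom Section 4.1 deliberately enrols; Section 8.2.2 separately allows deviation-based exclusion

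*Protocol*

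**What the plan says.** **Who is recruited.** Section 4.1 allows enrolment up to 4 weeks after treatment start and asks for consecutive recruitment. It adds: "This includes patients who have stopped cabozantinib treatment within their first 4 weeks to avoid selection bias". Section 4.5 makes clear that both start and stop may precede consent: "Patients who have started cabozantinib treatment up to 4 weeks before giving informed consent but stopped treatment during the 4 weeks may be included".

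**Who is analysed.** Section 8.1 defines a treated participant as "Enrolled participant who received at least one intake of" "cabozantinib during the study". Section 8.2 defines one combined FAS/Safety set: "All eligible participants treated with cabozantinib within this" study. Effectiveness (8.2.1), baseline description (8.4.1), PFS (8.4.3.2) and safety (8.4.4) all use it.

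**When the study begins.** Section 4.7 states: "The study observation period starts from participants signing the informed consent". The same section dates the start of the study as a whole from the first participant's consent.

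**Deviations.** Section 8.2.2 leaves the allocation rules to a data review meeting before database lock, and says that "based on minor or major protocol deviations recorded, participants may be excluded from the safety/FAS population".

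**The concern.** The recruitment rule and the population definition pull in opposite directions. Early stoppers are brought in as a safeguard against selecting patients who tolerate the drug. The analysis set can then be read as requiring an intake after consent, which removes the early stoppers who had already finished treatment.

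The result would be a set conditioned on still taking cabozantinib at consent, while DoT, PFS and AE collection all run from the first dose. Early toxicity and early failure would be under-represented in AE incidence, AE-related discontinuation, DoT, PFS and the FAS-denominator DCR and ORR. AEs would also be recorded for people outside the Safety set, because Sections 4.5 and 9.2.1 collect them from first intake.

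Section 8.2.2 is a second and independent weakness. It lets exposed participants be removed from a safety set for a minor deviation, against the Section 8.2 wording that takes in all eligible treated participants. On the planned calendar, interim analyses 2 and 3 report effectiveness before the final lock, and interim analysis 2 also reports safety. Nothing requires the allocation rules to be fixed before those results are seen.

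**Working it through.** **1. The plan's own figure.** Section 8.3 gives ±7.5% for n = 135 and an expected DCR of 73%. Evaluable n = 150 × 0.90 = 135. Half-width = 1.96 × √(0.73 × 0.27 / 135) = 0.0749, or 7.5 points. The pooled DCR is (51 + 94)/(64 + 134) = 145/198 = 73.2%. Both reproduce, so the sample-size arithmetic is not at issue.

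**2. Following one patient through the text.** A patient starts, stops ten days later and consents in week 3.
- 4.1 and 4.5: may be enrolled.
- 4.7: own observation begins at consent, after the last intake.
- 8.1: no intake once observation has begun, so not treated on the literal reading.
- 8.2: not in FAS/Safety.
- 8.4.3.1: the secondary DCR uses the FAS as denominator, so it does not bring the patient back.
- 4.5 and 9.2.1: AEs are collected from first intake all the same.

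A patient who consents while on drug and stops a few days later has an intake during the study and is kept on any reading.

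**3. How many could be affected.** The protocol does not give the share. Inputs: median DoT 5.5 months (epNET) and 8.3 months (pNET) from Section 2.3; 4 weeks = 0.92 months. Assumption: exponential treatment duration.
- epNET: 1 − 0.5^(0.92/5.5) = 11.0%.
- pNET: 1 − 0.5^(0.92/8.3) = 7.4%.
- Mix with 7.3% pNET (Section 8.5): 10.7%. Mix with 32% pNET (64/198, Section 8.3): 9.8%.
- Of 150: 15 to 16 participants. This is a ceiling, reached only if everyone consents at week 4.
- If consent is uniform over weeks 0-4, average 1 − e^(−λt) over that window, which gives 1 − (1 − e^(−x))/x with x = ln 2 × 0.92/median. This is 5.6% for epNET and 3.7% for pNET, or 5.0% to 5.4% mixed: 7 to 8 participants.
- If everyone consents at or before first dose: 0%.

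**4. Effect on the FAS-denominator DCR.** Assume 73.2% among those kept and no disease control among those lost. With a share f lost, DCR over all exposed = 0.7323 × (1 − f), and the overstatement is 0.7323 × f.

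| f | DCR, all exposed | Overstatement (points) |
|---|---|---|
| 0% | 73.2% | 0 |
| 2% | 71.8% | 1.5 |
| 5% | 69.6% | 3.7 |
| 10% | 65.9% | 7.3 |
| 10.7% | 65.4% | 7.8 |

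This is the worst case, since a patient who stopped for toxicity may have a scan showing stable disease.

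**5. Effect on safety rates.** If a share f is lost, with event rate q among those lost and r among those kept, the rate is understated by f × (q − r). This is at most f, so at most about 5 points at f = 5% and about 11 at the ceiling.

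**6. Precision.** Losing 5% or 10% of the 135 moves the half-width from 7.5 to 7.7 or 7.9 points. The interval width would give no warning.

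**7. The primary DCR.** Section 8.4.3.1 divides by FAS participants with at least one post-baseline tumour assessment, and Table 4-1 first schedules one at Month 3. An early stopper without an assessment is outside this denominator however the FAS is worded. The table in step 4 therefore does not measure bias in the primary endpoint.

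**The case against.** The strongest reply is that exclusion is only one reading. Section 8.1 does not tie the study to the participant's own consent, and Section 4.7 also starts the study at the first participant's consent. An intake before a later participant's consent would then fall within it. Much else supports an inclusive intention: Visit 1 can be captured retrospectively, AEs are collected from first intake, and DCR, ORR, PFS, DoT and TTNT all run from the first dose. This stands as far as it goes and makes the text ambiguous rather than a certain exclusion. It does not settle the matter, because one permissible reading still defeats a stated bias safeguard.

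Three stronger conclusions might be drawn, and the protocol does not support them:
- **That all early stoppers leave every analysis.** Only those whose last intake preceded consent are at risk. The Enrolled population keeps them, and Section 8.4.2 tabulates reasons for exclusion.
- **That Section 8.2.2 removes them.** Stopping within 4 weeks is expressly allowed, so it is not a deviation.
- **That the primary DCR is inflated by the amounts in the table.** Its denominator already requires a post-baseline assessment.

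Section 8 says the SAP may change its content, and the study is descriptive with no formal testing. Both lower the stakes, but neither reconciles the protocol's own sections.

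**Conclusion.** The point holds as a conflict between the recruitment rule (4.1, 4.5) and the definitions of treated and FAS/Safety (8.1, 8.2), left open by the two start dates in 4.7. On the literal reading, patients whose last intake preceded consent leave the effectiveness and safety outcome analyses.

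The size is uncertain. The affected share runs from near 0% to about 10-11%. The upper end rests on exponential treatment durations, the stated DoT medians and universal consent at week 4. Any distortion falls on the FAS-denominator DCR and ORR, DoT, PFS, and safety and discontinuation rates. For the FAS-denominator DCR it is at most about 8 points, if none of those lost had disease control. Early stoppers without a post-baseline assessment stay outside the primary DCR under either reading.

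The deviation clause in 8.2.2 is a separate defect. It contradicts the definition in 8.2, and its effect cannot be sized from the protocol.

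**What to change.** **Sections 8.1 and 8.2.** Define treated participants and the FAS/Safety set as all eligible enrolled participants with at least one cabozantinib intake since the treatment start recorded at Visit 1, including intakes up to 4 weeks before consent.

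**Section 8.2.2, as a separate change.** Delete exclusion from FAS/Safety for minor or major deviations. Exclude only for no intake, ineligibility or no valid consent, and examine deviations in a sensitivity set.

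**Cost.** Wording in three subsections. No new data are needed, since treatment start and AEs from first intake are already collected. Some rates may become slightly less favourable. The first change does not return early stoppers without a post-baseline assessment to the primary DCR, so the FAS-denominator DCR should be reported beside it, as Section 8.4.3.1 already plans.
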